2.4.2 ADVERSE EVENTS

Adverse events will be summarized overall, by severity, seriousness, and by relationship to investigational device. Adverse device effects and early withdrawals due to adverse events will be summarized separately. Ninety-five percent confidence intervals may also be provided for the comparison of serious adverse event rates between groups. Adverse events will be categorized by System Organ Class (SOC) and preferred term using MedDRA. The incidence of adverse events will be summarized overall and by SOC and preferred term using frequencies and percentages. Each subject will be counted only once for each of the incidence rates, regardless

of the number of occurrences (events) the subject experiences. The Safety population will be used.

2.4.3 DEVICE DEFICIENCIES

Inadequacy of medical device with respect to identity, quality, durability, reliability, safety and performance, including malfunctions and inadequate labeling will be presented in a data listing.

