2.6 Risk/Benefit of the Neurotech Vital Compact Device

2.6.1 Residual Risks Identified in Risk Analysis Report

As part of the risk analysis process conducted during development, all identified risks were subjected to review and were either eliminated or reduced to 'as low as reasonably possible' (ALARP) by changes in process, documentation and planned user training.

Potential risks under these ALARP categories include manufacturing, labelling, storage and user error problems.

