3.1 Primary Objective

The primary objective of this clinical study is to evaluate and compare the safety and performance profile of the Neurotech Vital Compact device (delivering electrical stimulation through external electrodes) and the itouch Sure Pelvic Floor Exerciser (delivering electrical stimulation through an internal vaginal probe) for the treatment of stress urinary incontinence following a 12-week treatment program.

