9.1 Adverse Events Definitions

Adverse Events:

Any untoward medical occurrence, unintended disease or injury, or untoward clinical signs (including laboratory findings) in subjects, users or other persons, whether or not related to the medical device.

Adverse Device Effects:

An adverse event related to the use of a medical device.

Device Deficiency:

An inadequacy of a medical device with respect to its identity, quality, durability, reliability, safety or performance. Device deficiencies include malfunctions, user errors and inadequate labelling.

Collection of Adverse Events:

Adverse events will be collected for randomized subjects only.

Serious Adverse Events (SAE):

An adverse event that:

- Led to death;
- Led to a serious deterioration in the health of a subject, that resulted in 1) a life threatening illness or injury, or 2) a permanent impairment of a body structure or a body function, or 3) in patient or prolonged hospitalisation or 4) medical or surgical intervention to prevent life threatening illness or injury or permanent impairment to a body structure or a body function
- Led to foetal distress, foetal death or a congenital abnormality or birth defect

Unanticipated Adverse Device Effects (UADE):

Any serious adverse effect on health or safety or any life-threatening problem or death caused by, or associated with, a device, if that effect, problem or death was not previously identified in nature, severity, or degree of incidence in the investigational plan or application (including a supplementary plan or application), or any other unanticipated serious problem associated with a device that relates to the rights, safety, or welfare of subjects.

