10.3 Statistical Methods

10.3.1 General Statistical Considerations

Data will be summarized using descriptive statistics. For continuous measures this will include mean, standard deviation, median, and range. For categorical measures, counts and percentages will be provided. Data will be summarized separately for each randomized arm under the principles of intent to treat, unless otherwise noted.

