10.3.8 Other Secondary Endpoints

Additional secondary endpoints will be summarized using descriptive statistics. There are no formal statistical tests associated with these endpoints, and no claims for labelling will be made.

The secondary endpoints that will be evaluated at 4 weeks and 26 weeks are as follows:

- Proportion of subjects considered to have achieved significant improvement, defined as a greater than 50% reduction in pad weight, from baseline on the provocative pad weight test;
- Urine leakage on the provocative pad weight test (following standardized bladder-filling protocol);
- Urine leakage experienced by the subject at home in the 24-hour pad weight test;
- Incontinence episodes/day recorded using a 7-day voiding diary;
- Proportion of subjects achieving dryness (<1g on the provocative pad weight test);

- Improvement in quality of life assessed using the Incontinence Quality of Life Questionnaire (I-QOL);
- Number of pads/day recorded using a 7-day voiding diary; and
- Dryness, defined as a pad weight of less than 1.3g on the 24-hour pad weight test (including an evaluation at 12 weeks).
- Proportion of subjects considered to have achieved significant improvement, defined as a greater than 50% reduction in pad weight, from baseline on the 24-hour pad weight test (including an evaluation at 12 weeks).

Other secondary measures to be evaluated are as follows:

- Proportion of subjects achieving dryness at Week 12 in each group (<1g on the provocative pad weight test).
- Within Neurotech Vital Compact group estimate of mean change, with respect to baseline, in sexual function as measured by the Pelvic Organ Prolapse/Urinary Incontinence Sexual Questionnaire (PISQ-IR) at Week 12;
- Between group comparison of mean change, with respect to baseline, in sexual function as measured by the Pelvic Organ Prolapse/Urinary Incontinence Sexual Questionnaire (PISQ-IR) at Week 12;
- Within Neurotech Vital Compact group estimate of patient response to the Patient Global Impression of Improvement (PGI-I) at Week 12.
- Between group comparison of patient response to the Patient Global Impression of Improvement (PGI-I) at Week 12;
- Safety in relation to adverse events and device deficiencies reported;
- Evaluation of reduction in urine leakage on the provocative pad weight test in relation to the mean intensity of the stimulation delivered during the 12-week treatment programme;

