10.3.9 Safety

Safety analyses will be performed on the Safety population.

Adverse events will be summarized overall, by severity, seriousness and by relationship to investigational device. Adverse device effects and early withdrawals due to adverse events will be listed and summarised separately. Adverse events will be collected for randomized subjects only.

Ninety-five percent confidence intervals may also be provided for the comparison of serious adverse event rates between randomized arms.

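### SAP 2.4.3 plans only a listing for device deficiencies and does not name user errors, so deficiencies that cause no adverse event get no planned by-device summary; SAP Section 4 declares neither change (minor).

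*SAP*

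**What the plan says.** **Protocol.** Section 10.3.8 lists, among the other secondary measures, "Safety in relation to adverse events and device deficiencies reported". The same section opens with the method: "Additional secondary endpoints will be summarized using descriptive statistics". It adds that no formal tests attach to these endpoints. Section 10.3.1 sets the default layout: "Data will be summarized separately for each randomized arm under the principles of intent to treat, unless otherwise noted". Section 9.1 gives the definition: "Device deficiencies include malfunctions, user errors and inadequate labelling". Section 2.6.1, on the Vital Compact, says: "Potential risks under these ALARP categories include manufacturing, labelling, storage and user error problems". The primary objective in 3.1 is to "evaluate and compare the safety and performance profile of the Neurotech Vital Compact device" and that of the itouch Sure. The dedicated safety section, 10.3.9, says "Adverse events will be summarized overall, by severity, seriousness and by relationship to investigational device" and is silent on deficiencies.

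**SAP.** Section 2.4 has three parts. Device use (2.4.1) is summarised for each device. Adverse events (2.4.2) are summarised with frequencies and percentages. Device deficiencies (2.4.3) follow the Protocol 9.1 definition closely, but the text ends: "including malfunctions and inadequate labeling will be presented in a data listing". User errors do not appear in it. The list of other secondary endpoints in SAP 2.3.4 does not carry the deficiency item either. Section 4 lists the changes from the protocol's methods and mentions neither the move to a listing nor the shorter wording.

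**The concern.** The trial compares two devices that women use on their own at home for 12 weeks. They are set up in different ways: two garments carrying eight electrodes, or a vaginal probe. Malfunctions and errors of use could therefore differ between them, and safety is part of the primary objective. The protocol promises a descriptive summary of deficiencies. The SAP, followed literally, produces rows in a listing and no totals. A programmer working from SAP 2.4.3 alone could also leave user errors out of the listing, because that is the one protocol example not carried over.

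What is at stake is a descriptive safety result in a study meant to supply data for regulatory clearance, and the record of why the plan changed. No efficacy conclusion depends on it.

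**Working it through.** The plan states no figure for deficiencies, so there is none to reproduce. The check is mainly a comparison of text.

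**Step 1: is there a protocol commitment to summarise?** Yes, but a general one. It comes from one item in 10.3.8, which combines adverse events with deficiencies, read with that section's opening sentence and the layout default in 10.3.1. Section 10.3.9 neither repeats nor withdraws it.

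**Step 2: what does the SAP change?**

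| Element | Protocol | SAP |
|---|---|---|
| Examples of a deficiency | Malfunctions, user errors, inadequate labelling (9.1) | Malfunctions, inadequate labelling (2.4.3) |
| Output | Descriptive statistics (10.3.8) | Data listing (2.4.3) |
| Split by group | Default by arm (10.3.1) | Not stated for the listing |
| Declared as a change | n/a | No (Section 4) |

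**Step 3: what is still summarised?** SAP 2.4.2 summarises adverse events by severity, seriousness and relationship to device. It summarises adverse device effects and withdrawals for adverse events separately. It uses the Safety population, which SAP 2.1 groups by device actually used. SAP 2.4.1 summarises sessions, duration, intensity and percentage of use. A deficiency that harms a woman therefore reaches a table through the adverse event. A deficiency without an adverse event does not.

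**Step 4: what could a by-device table show?** The input from the documents is 90 women per group (Protocol 10.2, SAP 1.4). Deficiency rates are not given, so a common rate p is assumed across a range. The 95% half-width for the difference is 1.96 × √(2p(1 − p)/90):

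| Assumed p | Half-width (percentage points) |
|---|---|
| 2% | 4.1 |
| 5% | 6.4 |
| 10% | 8.8 |
| 20% | 11.7 |

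For example, at p = 5%: 1.96 × √(2 × 0.05 × 0.95/90) = 1.96 × 0.0325 = 0.064. A table would be informative about large differences only.

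**Step 5: is any single illustration decisive?** No. Suppose 9 of 90 against 2 of 90 (assumed counts). The difference is 10.0% − 2.2% = 7.8 points, and the Newcombe 95% interval is 0.6 to 15.9, but Fisher's exact test gives p = 0.057. With 8 against 2, the Newcombe interval is −0.3 to 14.5. One event changes the reading.

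**The case against.** The strongest case against has four parts.

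- **User errors are not removed.** SAP 2.4.3 keeps the broad description of a deficiency and introduces its examples with a non-exhaustive word. Collection is governed by Protocol 9.1, which the SAP does not narrow. This stands. A reader might infer that user errors will go unreported; the text supports only that they are unnamed, which leaves room for doubt.
- **The protocol's commitment is weak.** Its own safety section plans no deficiency summary, and Protocol Section 10 leaves further detail to the SAP. This stands in part: the duty is general and descriptive. But 10.3.8 does list deficiencies, and a change from summary to listing belongs in SAP Section 4, which records matters as small as showing the race subgroup for one more outcome.
- **The safety comparison is not empty.** A reader might infer that the plan yields no by-device information on device problems. It does not go that far, as Step 3 shows. Section 2.6.1 also adds little: it concerns the Vital Compact alone and describes risks already eliminated or reduced as far as reasonably possible, so it sets up no comparison of user error between devices.
- **A listing can be counted.** If it shows the device, totals by device can be made by hand. If it is empty, the known denominator gives the same bound as a table: for 0 of 90, 1 − 0.025^(1/90) = 4.0%. So it would be wrong to say that a listing cannot support that bound. But the SAP does not state the listing's columns, and a hand count is not a pre-specified summary.

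**Conclusion.** The point holds in a limited form. The SAP replaces a descriptive summary of device deficiencies with a listing, leaves user errors unnamed, and declares neither change. As a result, deficiencies that cause no adverse event have no planned by-device summary.

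Severity is minor. The primary analysis, the key secondary hierarchy and the adverse event tables do not change. The size of any difference that might go unseen cannot be given, because the documents state no deficiency rate; the half-widths above rest on assumed rates and on 90 women per group being in the Safety population. The documents do not support a claim that user errors are excluded, that the safety comparison lacks by-device results altogether, or that the protocol requires an interval or test for deficiencies.

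**What to change.** In SAP 2.4.3:

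1. Add user errors to the named examples, to match Protocol 9.1.
2. Add one descriptive table on the Safety population, by device used: number and percentage of subjects with at least one deficiency, and number of events, overall and by type (malfunction, user error, labelling, other).
3. Keep the listing as support.

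A confidence interval for the difference is optional, since it goes beyond the protocol's descriptive commitment. If the sponsor prefers the listing alone, SAP Section 4 should say so and give the reason.

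The cost is two words and one table. Protocol 9.4 already requires deficiencies to be reported to the sponsor, so no new reporting stream is needed. The drawbacks are that counts may be small and that user-error reporting may vary by site, so the table should be read as description.

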2.5 INTERIM ANALYSIS FOR FUTILITY

An interim analysis for futility will be conducted when 90 subjects have Visit 4 (12 week) data available. The analysis will be conducted by an independent statistician. A conditional power will be calculated based on projecting the observed trend of the difference between the two groups in the primary efficacy parameter for subjects completing the study. If the analysis indicates that the conditional power for a positive outcome of non-inferiority is less than 30%, the independent statistician will communicate to a designated sponsor's representative that the study is unlikely to meet its primary objective. The sponsor may evaluate additional information and make a final decision regarding continuation of the study. The interim analysis will not be used to stop the study early for a positive outcome; therefore, no adjustment to the Type-1 error is indicated (Lachin, 2005).

The independent unblinded statistician will receive the interim study data and the randomization information confidentially from the CRO. Using the ITT population with multiple imputations for missing data, the conditional power will be calculated using the normal approximation to the binomial distribution, using the non-inferiority margin of 5% (where the lower limit of the two-sided 95% CI is greater than -5%). As a sensitivity analysis, the conditional power may also be calculated using LOCF for missing data. The independent statistician will communicate the findings directly with the designated sponsor's representative. All communications between the unblinded statistician and the sponsor's representative will be kept confidential and unknown to all personnel involved in the trial (e.g., other sponsor's personnel, CRO, and clinical center personnel).

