1.4 SAMPLE SIZE AND POWER

Sample size calculations were performed using the NQuery Advisor® version 5.0, under a two group test of proportions.

Research suggests that the response rates for Vital Compact and itouch Sure at 12 weeks will be 71% and 46%, respectively (itouch success rate based on Sand, 1995).

The sample size calculation is based on the assumption that the itouch Sure Pelvic Floor Exerciser success rate is 52% and the Vital Control success rate is 71%. A sample size of 87 subjects per group will provide 90% power using a one-sided Type I error rate of 0.025, and a non-inferiority margin of 5%. A randomization allocation of 1:1 was also assumed. For practical reasons, the sample size has been increased to a recruitment of 180 subjects (90 subjects per treatment group).

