2 ANALYSIS

2.1 ANALYSIS POPULATIONS

The primary analysis population will be the intent to treat (ITT) population. This will include all randomized subjects. Subjects will be summarized according to their randomized assignment. If there are randomized subjects who do not use the device at least once, a modified ITT (mITT) population will be defined to exclude such subjects and this population will be used in place of ITT.

A per-protocol (PP) population will also be evaluated for the primary endpoint. This population will consist of subjects who:

- Signed informed consent
- Met inclusion/exclusion criteria
- Were treated per randomized assignment
- Had 12 week outcome data available
- Met study compliance criteria
- No significant protocol deviations

Prior to locking the database, the PP criteria will be reviewed, additional criteria will be added if needed, and a listing of PP violations will be generated. The Sponsor/CRO will review this list and determine exclusions from this population. The final list of PP criteria and exclusions will be documented prior to unblinding.

The Safety population will include all randomized subjects who used the device at least once. Subjects will be summarized according to the actual device used, rather than the randomized assignment.

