2.3.2.1 PRIMARY ENDPOINT ANALYSIS

To test these hypotheses, the difference in the proportions of responders and a 95% Confidence Interval (CI) of the difference in proportion of responders will be calculated using the normal approximation to the binomial distribution. Non-inferiority will be claimed if the lower limit of

the 95% CI is greater than -5%. Furthermore, superiority will be claimed if the lower limit of the 95% CI is greater than 0%. The p-value for superiority will also be reported, based on a Chi-Square test. The total number of successes in each study arm will be summarized, along with the corresponding proportions and exact 95% CIs.

The ITT population will serve as the primary analysis population. For this analysis, if a subject does not complete the 12 week assessment, their outcome will be imputed using multiple imputations (Schafer, 1997). The multiple imputation methodology will be implemented as follows:

1. Ten imputed datasets will be generated to impute missing urine leakage using the below SAS code. Only the imputed values at Week 12 will be retained.

```
Proc MI NIMPUTE=10 SEED=20150930 MIN=0 0 0 MAX= . . .;  
  var base w4 w12;  
  fcs reg(base) reg(w4) reg(w12);  
run;
```

2. The ten imputed datasets will be analyzed separately. Using the methodology described above, the Week 12 urine leakage will be compared against the baseline weights to classify subject responders.
3. The proportion of responders in each treatment group, along with the associated standard error, will be calculated for each of the ten imputed datasets. The individual proportion estimates and standard errors will be pooled by treatment using the SAS code below.

```
Proc MIANALYZE;  
  modeleffects prop;  
  stderr se_prop;  
  by trt;  
run;
```

4. The difference in the proportions of responders and the standard error of the difference will be calculated for each of the ten imputed datasets. The individual estimates of the difference in proportions, as well as the associated standard errors of the differences, will be pooled using the SAS code below.

```
Proc MIANALYZE;  
  modeleffects prop_diff;  
  stderr se_diff;  
run;
```

A supportive analysis will also be conducted using similar methodology in the PP population.

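### Read literally, SAP 2.5 imputes women not yet due for Week 12 without regard to arm, which shrinks the interim difference and raises the chance of a false futility message

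*SAP*

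**What the plan says.** The trigger in SAP 2.5 is: "An interim analysis for futility will be conducted when 90 subjects have Visit 4 (12 week) data available". The analysis set and method follow in the section's second paragraph: "Using the ITT population with multiple imputations for missing data, the conditional power will be calculated using the normal approximation to the binomial distribution". If conditional power for non-inferiority is below 30%, an independent statistician tells one sponsor representative that success is improbable. The sponsor may look at further information and then decides whether to continue.

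Three other statements determine what this means in practice.

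- SAP 2.1 says of the ITT population: "This will include all randomized subjects". The modified version drops only women who never used the device.
- SAP 2.3.2.1 imputes any subject lacking a completed Week 12 assessment. Its imputation step lists "var base w4 w12", with no treatment variable and no BY statement. Treatment appears only later, when the imputed results are pooled.
- SAP 2.5, first paragraph (carried over from Protocol 10.3.10), describes the projection as using the trend among women who complete the study.

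The SAP gives no information fraction for the interim and no false-futility rate. Protocol 10.3.10 left the details of the interim to the SAP.

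**The concern.** When the 90th woman reaches Week 12, others will have been randomised within the previous 12 weeks. They have no Week 12 value because it is not yet due, not because it was lost. If they stay in the set and are imputed from a model that ignores arm, their imputed outcomes differ little between arms and pull the estimated difference towards zero. If they are also counted towards the information fraction, the calculation assumes less of the trial remains than is true, and the 30% rule becomes harder to pass.

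At stake is a misleading message about a device that performs as planned. Because the result is kept from other sponsor staff, the CRO and the sites, few people could question it.

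**Working it through.** **1. The plan's own sample size.** Inputs from SAP 1.4: "itouch Sure Pelvic Floor Exerciser success rate is 52% and the Vital Control success rate is 71" (per cent), margin 5 points, one-sided 0.025, 90% power. With p̄ = (0.71 + 0.52)/2 = 0.615:

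n = 2 p̄(1 − p̄)(1.960 + 1.282)² / (0.19 + 0.05)² = 86.4, so 87 per group.

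This agrees with the SAP: "A sample size of 87 subjects per group will provide 90% power using a one-sided Type I error rate of 0.025".

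**2. How many women are not yet due.** The protocol synopsis (Study duration) estimates 12 months of recruitment: 180/12 = 15 per month if uniform. Twelve weeks is 12/52 × 12 = 2.77 months, and 15 × 2.77 ≈ 42. So about 90 + 42 = 132 are randomised, of whom 42/132 = 32% would be imputed. Recruitment over 18 or 24 months gives 28 or 21 not yet due (118 or 111 randomised).

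**3. False-futility rate using only the 90 observed women.** Current-trend conditional power is Φ[(Z/√t − 1.960)/√(1 − t)], with Z = (d + 0.05)/SE.

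- At t = 90/180 = 0.5, conditional power is below 30% when Z < √0.5 × (1.960 − 0.524 × √0.5) = 1.124.
- With 45 per arm, SE = √[(0.71 × 0.29 + 0.52 × 0.48)/45] = 0.1006, so the expected Z is 0.24/0.1006 = 2.386.
- The flag probability is Φ(1.124 − 2.386) = 10.4%. Simulation gave 11.1%.

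**4. Size of the dilution.** If imputed women showed no difference between arms, the expected difference would be 0.19 × 90/132 = 0.130. Week 4 values restore a little of it.

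**5. Simulation of the literal reading** (4,000 trials, true rates 71% and 52%, 132 randomised, ten normal-regression imputations bounded at zero, Rubin's rules):

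| Interim analysis | Mean difference | Flag, t = 0.5 | Flag, t from Rubin variance | Flag, t = 132/180 |
|---|---|---|---|---|
| Observed women only | 0.189 | 11.1% | – | – |
| All randomised, imputed by arm | 0.181 | 10.0% | 12.0% | 16.9% |
| All randomised, imputed without arm | 0.134 | 14.1% | 19.0% | 27.0% |

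Against observed women only, the last row is 14.1/11.1 = 1.3, 19.0/11.1 = 1.7 and 27.0/11.1 = 2.4 times. Against by-arm imputation at the same t it is 1.4 to 1.6 times.

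The choice of t matters by itself. At t = 132/180 = 0.733 the flag threshold rises to Z < √0.733 × (1.960 − 0.524 × √0.267) = 1.45.

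**6. Sensitivity** (mostly 1,500 trials each; flag rates in the order of the three t columns):

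- 18-month recruitment: difference 0.147; flags 14.3%, 16.6%, 20.7% against 10.8% for observed women only.
- 24-month recruitment: difference 0.163; flags 11.2%, 12.8%, 15.7% against 9.6%.
- 10% dropout, 12-month recruitment: difference 0.127; flags 14.9%, 21.7%, 32.2% against 9.7%.
- True rates 71% and 46%: flags 5.4%, 7.3%, 10.7% against 4.1%.
- Week 4 correlation 0.3 to 0.8, a smaller or larger Week 4 effect, or a smaller spread of change: difference 0.133 to 0.140.

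**Assumptions not in the documents:** uniform accrual; log-normal baseline leakage (median about 15 g, restricted to 3–90 g); SD of the log ratio 0.6 to 1.0; the Week 4 correlation and effect; two-thirds of not-yet-due women having a Week 4 value. Sequential regression stood in for full FCS. Simulation error is about 0.5 to 1 point.

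**The case against.** The strongest reply is that nobody intends to impute women whose visit is still ahead. The completer wording in SAP 2.5 points that way, and the imputation rule in SAP 2.3.2.1 fits dropouts and missed visits at least as well as visits not yet due. Nor does SAP 2.5 say that the 2.3.2.1 code is the interim model.

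This has force, but it does not settle the matter. The more specific sentence, on the set and method, names ITT with imputation. The completer wording does not cleanly mean the 90 either, since participation runs to Week 26: at 15 per month, the 14 weeks between the two visits represent about 48 women, so only about 90 − 48 = 42 would have finished. If the 2.3.2.1 model is not meant, the interim has none. The optional LOCF check has the same difficulty, because a woman with no Week 4 value would carry her baseline forward and count as a non-responder in either arm.

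Several stronger inferences are tempting and not supported:

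- **False flags double.** The base-case increase is 1.3 to 2.4 times. It reaches two mainly when imputed women count fully as information, which the SAP neither says nor excludes.
- **The rule stops the trial.** The message is advisory and the sponsor decides.
- **The missing treatment term is the whole cause.** Imputing by arm with t = 132/180 still gives 16.9%, so part of the increase comes from overstating the information.
- **Recruitment will take 12 months.** That figure is an estimate. The synopsis anticipates a 28-month study, while 12 months plus about 30 weeks per woman (Protocol 8.6) is only about 19. Slower recruitment is plausible and weakens the effect.

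**Conclusion.** The concern holds as a conflict within SAP 2.5 whose literal reading is biased towards futility when the device is truly better. With uniform 12-month recruitment and the planning rates, the mean interim difference falls from about 19 to about 13 points. The false-futility chance rises from about 10–11% to 14–27%, with the unstated information fraction deciding where in that span it lies. With 18- or 24-month recruitment the difference is about 15 or 16 points. The direction was the same in every 71% versus 52% scenario examined; the size depends on accrual and on the assumed leakage model. The consequence is an avoidable risk of a misleading advisory message. The interim cannot be used to claim success, so this is not an argument that Type I error is inflated.

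**What to change.** In SAP 2.5, before the interim is run:

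1. Define the interim set as women who have a Week 12 assessment, have withdrawn, or have passed the Week 12 window. Exclude women not yet due, and align the completer wording with this.
2. Impute genuinely missing Week 12 values separately by arm, or with arm in the model, and say that this model applies at the interim.
3. State the information fraction: women with observed Week 12 data divided by 180, or a fraction derived from the Rubin's-rules variance. Withdrawn women without Week 12 data should not count as full information.
4. Apply the same set to the optional LOCF calculation.

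The cost is a few sentences and no change to visits or sample size. The downside is that Week 4 data from women not yet due go unused. In the base-case simulation that loses little: by-arm imputation of everyone gave 10.0% (t = 0.5) or 12.0% (variance-based t), against 11.1% using observed women only.
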